There is a need to understand menthol cigarette use, given the high rates of use among cigarette smokers and negative impact on morbidity and mortality. The purpose of this study is to evaluate whether switching menthol smokers to non-menthol cigarettes reduces the subjective reward of smoking and reduces smoking behavior and nicotine dependence. This study may help to inform federal policy regulations by the FDA to restrict menthol additives in tobacco products and reduce the appeal and addictive potential of these products.

SECTION VI: RESEARCH ALTERNATIVES AND ECONOMIC CONSIDERATIONS

1. Alternatives: What other alternatives are available to the study subjects outside of the research?

This is not a treatment study. Anyone interested in quitting smoking will be provided with a treatment referral and will not be eligible to participate in this study. All participants will receive information about available smoking cessation services at the end of the study.

2. Payments for Participation (Economic Considerations): Describe any payments that will be made to subjects, the amount and schedule of payments, and the conditions for receiving this compensation.

Participants will be compensated \$40 for the baseline intake appointment and will receive \$25 for each subsequent study visit (days 0-21) reach a maximum of \$140 for study visits. Participants will be incentivized to provide adherence measures and will earn additional weekly compensation (e.g., completing self-report assessments (\$10/week), and returning spent cigarette filters (\$10/week)). Total maximum compensation for completing study tasks including bonuses: \$300.

3. Costs for Participation (Economic Considerations): Clearly describe the subject's costs associated with participation in the research, and the interventions or procedures of the study that will be provided at no cost to subjects.

There are no costs for participation.

4. In Case of Injury: This section is required for any research involving more than minimal risk, and for minimal risk research that presents the potential for physical harm (e.g., research involving blood draws).

- a. Will medical treatment be available if research-related injury occurs? *Write here*
- b. Where and from whom may treatment be obtained? *Write here*
- c. Are there any limits to the treatment being provided? *Write here*
- d. Who will pay for this treatment? *Write here*
- e. How will the medical treatment be accessed by subjects? *Write here*

(a-e) If a participant is injured as a direct result of participation in this study, treatment will be provided. The participant and/or his or her insurance carrier will be expected to pay the costs of this treatment. No additional financial compensation for injury or lost wages is available. Participants will not waive their legal rights by participating in this study.

IMPORTANT REMINDERS

Will this study have a billable service? Yes No

A billable service is defined as any service rendered to a study subject that, if he/she was not on a study, would normally generate a bill from either Yale-New Haven Hospital or Yale Medical Group to the patient or the patient's insurer. The service may or may not be performed by the research staff on your study, but may be provided by professionals within either Yale-New Haven Hospital or Yale Medical Group (examples include x-rays, MRIs, CT scans, specimens sent to central labs, or specimens sent to pathology). Notes: 1. There is no distinction made whether the service is paid for by the subject or their insurance (Standard of Care) or by the study's funding

mechanism (Research Sponsored). 2. This generally includes new services or orders placed in EPIC for research subjects.

If answered, "yes", this study will need to be set up in OnCore, Yale's clinical research management system, for Epic to appropriately route research related charges. Please contact [contact]

Are there any procedures involved in this protocol that will be performed at YNHH or one of its affiliated entities?

Yes No

If Yes, please answer questions a through c and note instructions below.

- a. Does your YNHH privilege delineation currently include the **specific procedure** that you will perform? Yes No
- b. Will you be using any new equipment or equipment that you have not used in the past for this procedure? Yes No
- c. Will a novel approach using existing equipment be applied? Yes No

If you answered "no" to question 4a, or "yes" to question 4b or c, please contact the YNHH Department of Physician Services ([name]) for prior approval before commencing with your research protocol.

IMPORTANT REMINDER ABOUT RESEARCH AT YNHH

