3. **Research Plan:** Summarize the study design and research procedures using non-technical language that can be readily understood by someone outside the discipline. **Be sure to distinguish between standard of care vs. research procedures when applicable, and include any flowcharts of visits specifying their individual times and lengths.** Describe the setting in which the research will take place.

Overview: The proposed project will compare within-person effects of switching from menthol cigarettes to non-menthol cigarettes in current adult menthol smokers (n=30). The primary outcome of interest will be smoking behavior measured via daily monitoring and self-report. Self-reported smoking behavior will be verified by objective biomarkers of nicotine and menthol exposure and by asking participants to return all spent cigarette filters. We expect switching to a non-menthol cigarette will reduce smoking satisfaction and smoking behavior (e.g., fewer cigarettes per day, longer time to first cigarette in the morning) compared to a baseline period of smoking menthol cigarettes.

Settings: Participants will be recruited from the community. Research study visits will take place at our outpatient research offices ([name] CMHC or [name] SATU, New Haven, CT) or a location that is convenient for participants, such as their home or public place

Procedures:

Interested study candidates will be screened by telephone. Those meeting initial eligibility criteria will attend an in-person screening appointment to learn more about the research study, provide written informed consent, and complete intake measures. Eligible participants will then begin a four week monitoring period. Participants will be provided with free menthol cigarettes of their own usual brand to smoke for one week (Phase I, days 0-7) and then will be switched to non-menthol cigarettes for two weeks (Phase II, days 7-21). Participants will be provided with all cigarettes in both Phase I and II to control for the possibility of increased consumption due to free cigarettes (as seen in other studies,⁸) and to encourage adherence to smoking the specified cigarette. To enhance the naturalistic nature of the study, research staff will provide subjects with their usual brand of menthol cigarettes (Phase I), and then will switch them to a matched-brand non-menthol cigarette (Phase II). At the end of the study, we will provide information on tobacco treatment programs to all participants.

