Screening Assessments: To screen for eligibility, participants will complete several assessments: 1) Cigarette preference questions assess current use of menthol cigarettes (i.e., “what brand of cigarettes do you prefer?” “what brand of cigarettes do you normally smoke?”). 2) Smoking history to assess smoking quantity and frequency such as number of cigarettes per day and number of years smoked. 3) Expired breath carbon monoxide (CO) measured in parts per million to confirm smoking status. 4) Drug use: to confirm participants are not currently using other substances (other than caffeine or nicotine) assessments will include i) a time-line follow-back interview to assess self-reported drug use quantity and frequency, ii) urine drug toxicology screens, and iii) current blood alcohol level measured with a breathalyzer.

Visit Assessments: Eligible individuals will complete self-report assessments at baseline and research visits: 1) Nicotine dependence, measured by 1) Time to first cigarette in the morning as an index of smoking reinforcement^{9,10}, 2) Fagerstrom Test for Nicotine Dependence⁹ and Wisconsin Inventory of Smoking Dependence Motives^{11,12} to assess multiple dimensions of tobacco dependence such as automaticity, loss of control, and affective enhancement. Additional

assessments include: 3) Questionnaire on Smoking Urges-brief ¹³ to measure cigarette craving, 4) Wisconsin Smoking Withdrawal Scale ¹⁴, to assess 7 constructs of nicotine withdrawal: anger, anxiety, concentration, craving, hunger, sadness, and sleep and 5) Confidence and interest in quitting smoking, rated from 1 (not at all) to 10 (extremely) and 6) measures of smoking behavior and cigarette reinforcement and satisfaction.

Biological Measures: Biomarkers of cigarette and menthol exposure will be collected at baseline and weekly research visits (day 7, 14, 21) to examine changes from baseline and to corroborate self-reported tobacco product use and menthol exposure during the trial. 1) Expired breath carbon monoxide (CO) measured in parts per million, 2) Urine cotinine to quantify nicotine exposure, 3) Menthol glucuronide measured in the same urine sample as a marker of menthol exposure.

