Adherence: Adherence to use of the specified cigarettes in Phase I and II will be closely monitored via subjective and objective measures. Participants will report the total number of cigarettes consumed each day and will be instructed how to save and return spent cigarette filters so the count can be verified by research staff, a procedure that has been utilized previously to verify adherence ¹⁵. Biological measures will monitor menthol exposure and can be compared between Phase I and Phase II to quantify reductions in menthol exposure. We aim to restrict access to menthol cigarettes during Phase II by recruiting only smokers who do not currently live with menthol smokers, collecting any remaining mentholated cigarettes from participants before switching to non-menthol cigarettes, and providing free cigarettes to discourage substitution. Additionally, we will assess participants' use of other mentholated products (e.g., mint toothpaste or gum) or other extraneous tobacco products that are not a part of the study (e.g., e-cigarettes, other tobacco products) each week during the trial. This will allow us to estimate any compensatory menthol or tobacco product use during the switching phase of the study. Lastly, we will incentivize participant reporting by providing compensation for returning spent cigarette filters.

4. **Subject Population:** Provide a detailed description of the types of human subjects who will be recruited into this study.

We will recruit current adult (at least 18 years old) daily smokers who report smoking at least 5 cigarettes per day for at least the past 6 months. See detailed inclusion and exclusion criteria below.

5. **Subject classification:** Check off all classifications of subjects that will be specifically recruited for enrollment in the research project. Will subjects who may require additional safeguards or other considerations be enrolled in the study? If so, identify the population of subjects requiring special safeguards and provide a justification for their involvement.

 Children	 Healthy	 Fetal material, placenta, or dead fetus
 Non-English Speaking	 Prisoners	 Economically disadvantaged persons
 Decisionally Impaired	 Employees	 Pregnant women and/or fetuses

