The principal investigator is responsible for monitoring the data, assuring protocol compliance, and conducting the safety reviews at the specified frequency monthly. During the review process the principal investigator will evaluate whether the study should continue unchanged, require modification/amendment, or close to enrollment. The principal investigator and the Institutional Review Board (IRB) have the authority to stop or suspend the study or require modifications.

- ii. What will the multi-site process be for protocol modifications? N/A this is a single-site study

9. **Statistical Considerations:** Describe the statistical analyses that support the study design.

Data analyses will be conducted with SPSS software. Effect size estimates with 95% confidence intervals will be constructed for each aim to inform future studies. The primary statistical analyses will use within-person repeated measures to test for differences in smoking behavior (e.g., number of cigarettes per day, nicotine dependence) in menthol versus non-menthol phases.

Justification for sample size: Estimation of sample size (n=30) is based on achieving a clinically meaningful precision in effect size estimates for the primary outcome of interest. A power analysis based on $\alpha=.05$ and $\beta=.80$ suggests a sample size of 30 subjects is sufficiently powered to detect medium or large effects ($d>.50$) within-person. Although we will be unable to detect smaller effects, this sample size is reasonable for a pilot study, and data will be used to test the feasibility of the paradigm and adherence monitoring methodology and to estimate effect sizes to inform the optimal sample size for a larger follow-up study.

Data Monitoring: Procedures for data collection, data management, monitoring of data quality and data analysis have been developed and refined in our previous tobacco studies. An experienced data analyst and the PI will supervise these procedures which include use of a computerized database to monitor research activities, screening and enrollment, compliance with protocol, completion of scheduled assessments, and data retrieval. Data quality will be ensured by: 1) extensive training/supervision of research staff in data collection; 2) preliminary review of all assessment instruments prior to data entry and checks for completeness and coding errors; 3) double data entry of written assessment instruments; 4) error-checking statistical programs.

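### Does it matter that the primary outcome is given as smoking behavior, with no single variable and no averaging window named?

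*Combined protocol and SAP*

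**What the plan says.** Section I.3 (Overview) defines the primary outcome as a construct: "The primary outcome of interest will be smoking behavior measured via daily monitoring and self-report". The examples that follow are "e.g., fewer cigarettes per day, longer time to first cigarette in the morning".

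Section I.9 applies the primary analyses, by within-person repeated measures, to "differences in smoking behavior (e.g., number of cigarettes per day, nicotine dependence) in menthol versus non-menthol phases". It justifies 30 participants by the precision of "effect size estimates for the primary outcome of interest", in the singular, and gives as one use of the data "to estimate effect sizes to inform the optimal sample size for a larger follow-up study". It also promises effect sizes with 95% confidence intervals for each aim.

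Section I.3 says how often each candidate is measured. Under Adherence: "Participants will report the total number of cigarettes consumed each day". Under Visit Assessments: "Eligible individuals will complete self-report assessments at baseline and research visits", and the list there opens with "Nicotine dependence, measured by 1) Time to first cigarette in the morning", followed by the Fagerstrom and Wisconsin instruments.

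Section I.1 (Aim 1) names cigarettes per day, dependence and quitting motivation as the expected changes, and says the pilot data will give effect sizes for these outcomes, in the plural, to plan larger studies.

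**The concern.** A primary outcome should be one variable with one summary rule, fixed before the data are seen. Here the label covers at least a daily count and a dependence measure, and dependence has three instruments. The examples are open-ended and unranked, while the sample-size paragraph speaks as if a single variable had been chosen. The rule for turning daily counts into a phase value is also unwritten, and day 7 belongs to both phases as the Procedures define them (days 0-7 and days 7-21).

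At stake is the estimate carried into the next study. If the team looked at several effect sizes and sized the follow-up on the most favorable one, that value would be biased upward and the follow-up underpowered. Familywise error matters less, because the pilot is meant to report several effect sizes with intervals.

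**Working it through.** **1. The plan's own figure.** Inputs from Section I.9: alpha .05 (taken as two-sided), .80 (printed as beta, read as power), d = .50, one within-person comparison.

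- Normal approximation: n = ((1.960 + 0.842)/0.50)² = 31.4, rounded up to 32.
- Power at n = 30: Φ(0.50 × √30 − 1.960) = Φ(0.779) = 78.2%.
- Smallest d at 80% power with n = 30: 2.802/√30 = 0.51.
- Exact paired t: n = 34, power 75.4% at n = 30, smallest d 0.53.

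So 30 fits one two-sided test at .05 by the normal approximation, to within 2 participants. The calculation uses a standardised d and no standard deviation for any particular outcome. It therefore reads the same whichever variable is called primary.

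**2. Which variable is meant.** Set the sections side by side:

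| Feature | Cigarettes per day | Nicotine dependence |
|---|---|---|
| Measured daily (I.3, Adherence) | yes | no; baseline and visits |
| Position in the Aim 1 list (I.1) | first | second |
| Position in the Overview examples (I.3) | first | second, as time to first cigarette |
| Position in the primary-analysis examples (I.9) | first | second |

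The Overview ties the primary outcome to daily monitoring. The count is the only candidate described as reported each day.

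**3. Which days.** Section I.9 states the contrast as menthol against non-menthol phases. Averaging each person's counts over each whole phase is the natural reading. Day 7 is one day. Adding one count x to the mean m of k other days moves that mean by (x − m)/(k + 1). With days 0-6 as the other menthol days (k = 7), the shift is one eighth of the departure. With days 8-21 as the other non-menthol days (k = 14), it is one fifteenth.

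**4. Size of the feared bias.** The documents give no correlations and no true effects, so all of this is assumption. Take two measures, n = 30, small-sample-corrected d, 60,000 simulated draws, and the larger estimate used. Let r be the correlation between the two change scores. The follow-up is sized by the exact paired t-test, two-sided .05, 80% power.

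| Both true d = .50 | r = .9 | r = .5 | r = 0 |
|---|---|---|---|
| Expected larger estimate | .54 | .58 | .61 |
| Follow-up n (34 if sized on .50) | 30 | 26 | 24 |
| True power at d = .50 (80.8% with 34) | 75% | 69% | 65% |

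Equal true effects are an unfavorable case. With true d of .50 and .30, the excess of the selected estimate over that measure's own true d is about .003 (r = .9), .05 (r = .5) and .08 (r = 0). With .50 and .20 it is about 0, .02 and .06. For scale, a single prespecified estimate at n = 30 has a standard deviation of about .20.

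**The case for a change.** The strongest reply is that the text does put nicotine dependence inside the primary analyses, so a reader could not object if it became the headline. Accepting cigarettes per day still leaves the day window unwritten. The pilot's purpose is to inform a larger study, which is where selection would do harm: under equal true effects the follow-up falls below 80% power even at r = .9. Naming the variable would cost a sentence or two.

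The textual part stands: neither the variable nor the averaging rule is written down. The harm does not follow from it. It needs the follow-up to be sized on the largest estimate, and no section says that. Aim 1 and Section I.9 commit to reporting the estimates, so a reader would see cigarettes per day beside the dependence measures with their intervals, and selection would be visible. The low cost is real, but the gain is small too: no data, sample size or power figure would change.

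The window argument also leans on a different problem. Section I.1 gives the menthol period as two weeks, and the Procedures in Section I.3 give one week. Those passages must be reconciled, but as a schedule contradiction in its own right. Within Section I.3 the phase days and the biomarker visits run to day 21, as do the payments in Section VI.2.

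**Conclusion.** No change to the plan follows. The primary variable is left unlabelled, but the daily-monitoring wording and the order of every example list point to cigarettes per day. The phase contrast is stated, and an analyst would average the daily counts by phase and report the dependence measures alongside. Allocation of day 7 moves a phase mean by at most one eighth of that day's departure from the mean of the other days.

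The possible bias in the effect size is .04 to .11 if two measures share a true d of .50 and the larger is chosen. It is smaller when the true effects differ (.003 to about .08 for .50 and .30), and it does not arise if the follow-up is sized on the cigarette count. These figures rest on assumed effects, assumed correlations and a selection rule absent from the plan. The conclusion rests on the plan's commitment to report effect sizes with 95% confidence intervals for these outcomes. It would weaken if only one estimate were reported without saying why it was chosen.

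### Time to first cigarette, an example of the primary smoking-behaviour construct, is scheduled only at baseline and visits; one added daily item could sharpen its phase comparison at almost no cost

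*Combined protocol and SAP*

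**What the plan says.** Section I, item 3 (Research Plan), Overview, defines the primary outcome broadly: "The primary outcome of interest will be smoking behavior measured via daily monitoring and self-report". Two sentences later it states the expected effect as a reduction in "smoking behavior (e.g., fewer cigarettes per day, longer time to first cigarette in the morning) compared to a baseline period" of menthol smoking. Time to first cigarette is one of the two examples given there.

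Visit Assessments, in the same item, places the measure differently: "Eligible individuals will complete self-report assessments at baseline and research visits: 1) Nicotine dependence, measured by 1) Time to first cigarette in the morning". It is scheduled at visits and listed first under dependence.

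The only text that describes a daily report is under Adherence: "Participants will report the total number of cigarettes consumed each day". No section provides for a daily record of time to first cigarette.

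Visit dates come from Biological Measures, where samples are "collected at baseline and weekly research visits (day 7, 14, 21"). Procedures has participants given their own menthol brand "to smoke for one week (Phase I, days 0-7") and then "switched to non-menthol cigarettes for two weeks (Phase II, days 7-21").

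Item 9 (Statistical Considerations) compares the menthol and non-menthol phases by within-person repeated measures. Its examples are cigarettes per day and nicotine dependence; time to first cigarette is not named.

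**The concern.** Cigarettes per day has up to 7 values in Phase I and 14 in Phase II. Time to first cigarette, named beside it as an expected behavioural change, has as few as one and two. No item wording or reference window is given for the visit question, so the reader cannot tell whether an answer describes that morning, the past week or a usual day. If it reflects about one day, variation between days (workdays and weekends, for example) goes almost undamped into the phase difference.

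The pilot is meant to supply effect sizes for a larger study. Measurement noise inflates the standard deviation of the within-person difference and so lowers the standardised effect passed on. Participants already report daily, so this noise may be avoidable.

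**Working it through.** **The plan's own figure.** The protocol gives no standard deviation, correlation or precision target for time to first cigarette. Its one design calculation is 30 participants for a within-person d above .50 at alpha .05 and power .80 (printed as beta). The two-sided normal approximation gives n = ((1.960 + 0.842)/0.50)² = 31.4, so 32, with 78.2% power at n = 30. The paired t calculation gives 34, with 75.4% power at n = 30. The figure is roughly reproduced and is not disputed here, but it leaves little slack.

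**Inputs.**
- Phase I is days 0-7, taken as 7 daily values; Phase II is days 7-21, taken as 14 (Procedures).
- Visits are at baseline and days 7, 14 and 21 (Visit Assessments; dates from Biological Measures).
- A separate day 0 visit is possible. Section VI, item 2 pays $40 for intake and $25 per later visit up to $140, and (140 − 40)/25 = 4 visits, which fits days 0, 7, 14 and 21.
- Assumptions not in the documents: day-to-day standard deviation s within a person, independent days, and a visit answer about as noisy as one day.

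**Formula.** With m1 menthol and m2 non-menthol values, the day-to-day part of the error of one person's phase difference is s × sqrt(1/m1 + 1/m2).

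| Source | m1 | m2 | Error | Reduction with daily entries |
|---|---|---|---|---|
| Daily entries | 7 | 14 | sqrt(1/7 + 1/14) = 0.46s | – |
| Visits: day 7 v days 14, 21 | 1 | 2 | sqrt(1 + 1/2) = 1.22s | 1 − 0.463/1.225 = 62% |
| Baseline also counted | 2 | 2 | sqrt(1/2 + 1/2) = 1.00s | 1 − 0.463/1.000 = 54% |
| Baseline and separate day 0 counted | 3 | 2 | sqrt(1/3 + 1/2) = 0.91s | 1 − 0.463/0.913 = 49% |

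**Lower end.** If each visit answer were a perfect average of the preceding week, the day 7 answer would equal the mean of 7 daily values, and days 14 and 21 together the mean of 14. The error would be 0.46s either way, and the gain 0.

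**Equal correlation between occasions.** Replace s by SD × sqrt(1 − ρ). For one against two visits the factor is 0.87 at ρ = .5 and 0.39 at ρ = .9; for daily values it is 0.33 and 0.15. The ratio is 1.225/0.463 = 2.6 at any ρ, because (1 − ρ) cancels.

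**Schedule.** Item 1 (Statement of Purpose) gives two menthol weeks, and Procedures also mentions four weeks of monitoring; neither fits days 0-21. With two menthol weeks and weekly visits in both phases, visits give sqrt(1/2 + 1/2) = 1.00s and daily entries sqrt(1/14 + 1/14) = 0.38s. The reduction is again 62%, so the point does not depend on which schedule applies.

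**The case against.** A reader might infer that the plan contradicts itself by promising daily measurement of something it collects only at visits. The text does not support that. The overview names two sources, daily monitoring and self-report, and a visit answer fits the second. Nowhere is time to first cigarette said to be monitored daily.

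A reader might also infer that one change in this item would be counted as confirming three Aim 1 hypotheses, because it is linked to behaviour, dependence and reinforcement. Aim 1 never mentions it. The behaviour hypothesis there is cigarettes per day, dependence also has the Fagerstrom and Wisconsin scales, and reinforcement has its own visit measures. Nor do the documents support taking the item out of the dependence measures: that placement is a referenced choice, and the cited paper's title links the item to dependence.

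Several cautions stand:
- That the daily report holds nothing but a count is an inference from silence; the Adherence text does not list the whole form.
- That the visit answer is a recall is also inferred.
- Baseline is a menthol assessment too, so one against two is not the only count. It precedes the free study cigarettes, however, and Procedures supplies cigarettes in both phases precisely to control for their effect.
- The measure is an example in a statement of expected effects, not the sole primary endpoint, and cigarettes per day is unaffected.
- The range of gain includes zero.

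These points limit how strongly the concern can be put. They do not argue against adding the item.

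**Conclusion.** The point holds as a cheap improvement to the precision of a named behavioural outcome, not as an error in the plan. As written, time to first cigarette is scheduled only at baseline and visits, which leaves one menthol-phase and two non-menthol-phase assessments on study cigarettes under the days 0-21 schedule.

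The 0 to 62% range (upper end 54% or 49% under the wider menthol counts) applies only to the day-to-day part of the error. Differences between people in how they respond to switching are not reduced by more measurements, and the documents do not give the share of each. The upper figures also need entries to be made on the day they describe. In a 30-person pilot whose main behavioural count is already reported daily, the consequence is moderate.

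**What to change.** 1. Add one item, minutes from waking to first cigarette, to the daily report participants already complete. If it is already on the form, say so.
2. Record a day without a cigarette as such, not as missing, and state how the analysis treats it. If switching works as expected, dropping those days would remove the most informative ones.
3. Use the daily entries for the Phase I versus Phase II comparison of time to first cigarette. Keep the visit item within the dependence measures as planned.
4. State the visit item's reference window, and whether baseline or Phase I is the comparator for it.
5. Reconcile the days 0-21 schedule with the two-week menthol period in the Statement of Purpose and the four-week monitoring period in Procedures.

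The cost is a few seconds of extra reporting per day and some wording changes. No visit, staffing or payment change is needed.
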